10.4.1.3 Considerations for all Analyses

In the unlikely event of an error in randomization or study drug administration, subjects will be grouped by the formulation they actually received in Safety, CC, and PP analyses but will be grouped by their intended randomized assignment in ITT analyses.

Subjects who receive treatment with an antibiotic active against CT for any reason before a particular post-baseline visit (Day 15 for analyses at Day 15, and Day 29 for analyses at Day 29) will be included in ITT and CC analyses as microbiologic failures and reviewed by the blinded case committee for inclusion in PP analyses.

Other subgroup analyses may be performed; details will be provided in the SAP.

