3.3. Study Definitions and Derived Variables

3.3.1. Microbiologic Cure Status at Visit 3

Microbiologic cure will be based on rectal CT NAAT results. For the primary analysis, microbiologic cure at Visit 3 (Day 29) will be defined using the criteria in [Table 1](#) below.

Table 1: Interpretation of Rectal CT NAAT Results for Day 29 Analyses

Visit 2 (Day 15) NAAT Result	Visit 3 (Day 29) NAAT Result	Clinical Interpretation at Visit 3 (Day 29)	Microbiologic Cure Status for Primary Analysis
Negative	Negative	Cure	Cure
Negative	Positive	Reinfection or Recrudescence	Failure
Negative	Unknown	Unknown	Unknown
Positive	Negative	Delayed RNA clearance	Cure
Positive	Positive	Failure	Failure
Positive	Unknown	Unknown	Unknown
Unknown	Negative	Cure or Delayed RNA clearance	Cure
Unknown	Positive	Reinfection or Recrudescence	Failure
Unknown	Unknown	Unknown	Unknown

Subjects will be classified as non-evaluable if they:

- did not return for Visit 3, or
- their NAAT results at Visit 3 were not available for any reason, or
- they could not be evaluated for microbiological outcome status at Visit 3 for any other reason.

3.3.2. Microbiologic Cure Status at Visit 2

Microbiologic cure status at Visit 2 (Day 15) will be defined using the criteria in [Table 2](#) below.

Table 2: Interpretation of Rectal CT NAAT Results for Day 15 Analyses

Visit 2 (Day 15) NAAT Result	Clinical Interpretation at Visit 2 (Day 15)	Microbiologic Cure Status for Secondary Analysis
Negative	Cure	Cure
Positive	Failure	Failure
Unknown	Unknown	Unknown

Subjects will be classified as non-evaluable if they:

- did not return for Visit 2, or
- their NAAT results at Visit 2 were not available for any reason, or
- they could not be evaluated for microbiological outcome status at Visit 2 for any other reason.

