6. GENERAL STATISTICAL CONSIDERATIONS

6.1. General Principles

Tabulations will be used extensively to summarize the data. All continuous variables will be summarized using the following descriptive statistics: n (sample size), mean, standard deviation, median, maximum and minimum. The frequency and percentages (based on the sample size) of observed levels will be reported for all categorical measures. Wilson confidence intervals for binomial proportions and difference in binomial proportions will be computed for efficacy variables. For the hypothesis tests comparing treatment groups with respect to efficacy outcomes, the two-sided Pearson Chi-Square test will be used. A 5% two-sided significance level will be used; i.e. two-sided 95% confidence intervals will be generated.

All summary tables will be structured with a column/sub-table for each treatment group (Azithromycin, Doxycycline, and All Subjects). In general, all data will be summarized by treatment group and/or site, and when appropriate by visit number. The total population size relevant to that table/column if applicable, including any missing observations will be displayed in the tables.

Data listings will be provided for all data. Note that in the data listings, Subject ID is the unique subject identifier, not the Study ID used on study and dates will not be included, only Study Day.

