6.1.1. Pseudo Code

The following SAS® pseudo code will be used to calculate the following:

Chi-Square test at 5% two-sided significance level and odds ratio (and 95% asymptotic CI):

```
proc freq;
  Table treatment*analysis_variable / chisq;
  ods output ChiSq=outputdsn1;
  ods output RelativeRisks=outputdsn2;
run;
```

Fisher's Exact test at 5% two-sided significance level:

```
proc freq;
  Table treatment*analysis_variable / exact;
  ods output FishersExact=outputdsn;
run;
```

95% Wilson CI for proportions/percentages:

```
proc freq;
  Table treatment*analysisvariable / binomial(wilson);
  ods output binomialcls=outputdsn;
run;
```

95% Wilson CI for difference in proportions (produces Newcombe CI):

```
proc freq;
  Table treatment*analysisvariable / riskdiff(cl=Wilson);
  Exact Riskdiff;
  ods output pdiffcls=outputdsn;
run;
```

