6.3.2.4. Considerations for Analysis Populations

In the unlikely event of an error in randomization or study drug administration, subjects will be grouped by the formulation they actually received in Safety, CC, and PP analyses but will be grouped by their intended randomized assignment in ITT analyses.

Before unblinding, a blinded case review committee will review subjects with a reported concomitant infection/disease/procedure that may interfere with study drug, use of concomitant medications or products that may interfere with study drug, significant protocol deviations, treatment adherence, and other events that may impact study drug effectiveness or study analyses. On a case-by-case basis, the case review committee will determine if each subject will be included in the PP population, if and when a subject should be censored or removed from PP analyses, and/or any other analytical requirements for the subject. The committee will be blinded to both treatment group and outcome status for each case.

Subjects who receive treatment with an antibiotic active against CT for any reason before a particular post-baseline visit (Day 15 for analyses at Day 15, and Day 29 for analyses at Day 29) will be included in ITT and CC analyses as treatment failures and reviewed by the blinded case committee for inclusion in PP analyses.

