8. EFFICACY EVALUATION

8.1. Interim Analysis

The primary efficacy endpoint for the interim analysis is the proportion of subjects with microbiologic cure in each study arm at Day 29. See Section 3.3.1 for the definition of microbiologic cure.

A test of hypothesis comparing the proportion of subjects with microbiologic cure at Visit 3 (Day 29) in each treatment group will be conducted in the CC population. The null hypothesis for the comparison is that there is no difference in proportions between treatment arms, with a two-sided alternative that considers the possibility of a difference in either direction. The test will be conducted using a Pearson Chi-Square test at the 5% two-sided significance level. The resulting test statistic will be compared to the O'Brien Fleming bound calculated in the study's sample size calculations. At the interim point the bound is |2.79651|, thus if the test statistic is either greater than 2.79651 (Group A cure rate is higher than Group B cure rate) or less than -2.79651 (Group B cure rate is higher than Group A cure rate), then the resulting action should be to stop the trial. Otherwise, the resulting action should be to continue on to the full sample size.

The proposed summaries to be generated for the interim analysis were approved by the DSMB at the organizational meeting on 30MAY2018 and they are copied in this SAP. The summaries will be semi-blinded, where the treatment group labels will be "Group A" and "Group B". Table 11 will summarize eligibilities for and reasons for exclusion from the CC population for all randomized subjects. Table 12 will present the microbiological cure rates with confidence intervals by treatment group. Also included is the test statistic and the O'Brien Fleming critical value.

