Table 7: Safety, Complete Case, and Per-Protocol Analysis Population Eligibilities by Treatment Group

Analysis Populations	Eligibility Category	Reason Subjects Excluded	Azithromycin (N=X)		Doxycycline (N=X)		All Subjects (N=X)	
			n	%	n	%	n	%
Safety Analysis Population	Eligible for Safety Population		x	x	x	x	x	x
	Excluded from Safety Population	Any Reason	x	x	x	x	x	x
Complete Case (CC) Analysis Population	Eligible for CC Population		x	x	x	x	x	x
	Excluded from CC Population	Any reason	x	x	x	x	x	x
Per-Protocol (PP) Analysis Population	Eligible for PP Population	Did not meet all inclusion/exclusion criteria	x	x	x	x	x	x
		Did not have a positive baseline rectal CT NAAT result	x	x	x	x	x	x
	Excluded from PP Population	Post-baseline microbiologic data not available at Visit 2 (Day 15)	x	x	x	x	x	x
		Post-baseline microbiologic data not available at Visit 3 (Day 29)	x	x	x	x	x	x
			x	x	x	x	x	x
		Any reason	x	x	x	x	x	x
		Did not meet all inclusion/exclusion criteria	x	x	x	x	x	x
		Did not have a positive baseline rectal CT NAAT result	x	x	x	x	x	x
		Post-baseline microbiologic data not available at Visit 2 (Day 15)	x	x	x	x	x	x
		Post-baseline microbiologic data not available at Visit 3 (Day 29)	x	x	x	x	x	x
		Received treatment for a symptomatic STD other than CT	x	x	x	x	x	x
		Exposed to an STD	x	x	x	x	x	x
		Received treatment with an antibiotic active against CT	x	x	x	x	x	x
		Had condomless receptive anal sex	x	x	x	x	x	x
		Did not sufficiently adhere to study drug	x	x	x	x	x	x

Note: N=Number of enrolled subjects randomized to the specified treatment group.

Table 8: Ineligibility Summary of Screen Failures

Category	Inclusion/Exclusion Criterion	n ^a	% ^b
Screen Failures	Number of screen failures	x	100
	Number of subjects failing any eligibility criterion	x	x
	Number of subjects declining enrollment	x	x
Failed Inclusion	Any inclusion criterion	x	x
	[inclusion criterion 1]	x	x
	[inclusion criterion 2]	x	x
	[inclusion criterion 3]	x	x
Failed Exclusion	Any exclusion criterion	x	x
	[exclusion criterion 1]	x	x
	[exclusion criterion 2]	x	x
	[exclusion criterion 3]	x	x
Declined Enrollment	Time commitment	x	x
	Concern of potential risks	x	x
	Number of procedures	x	x
	Unable to contact subject	x	x
	Other	x	x

^a More than one criterion may be marked per subject.^b Denominator for percentages is the total number of screen failures.

Table 9: Subject Disposition by Treatment Group

Subject Disposition	Azithromycin (N=X)		Doxycycline (N=X)		All Subjects (N=X)	
	n	%	n	%	n	%

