Eligible for CC Analysis Population		x	x	x	x	x	x
Excluded from CC Analysis Population	Any Reason	x	x	x	x	x	x
	Reason 1	x	x	x	x	x	x
	Reason 2	x	x	x	x	x	x
	...	x	x	x	x	x	x

Notes: Denominator for percentages is the number of subjects enrolled (N) in the study randomized to the specified treatment group.

Subjects will be counted for a particular reason for exclusion if they met the criterion. As subjects may meet more than one criterion, the sum of the individual reasons may add up to more than the subjects excluded.

Table 12: Interim Analysis Microbiological Cure Rates – CC Population

Treatment Group	Number of Subjects	Number of Subjects with Microbiologic Cure	Interim Microbiologic Cure Proportion	Interim Confidence Interval	Test Statistic	Critical Value
Group A	x	x	0.xx	0.xx, 0.xx	x.x	+/- 2.79651
Group B	x	x	0.xx	0.xx, 0.xx		

Implementation Notes:

Depending on the observed test statistic value, the last two columns will be rounded accordingly. The appropriate critical value (positive vs. negative) will be displayed according to the sign of the test statistic.

Table 13: Microbiologic Cure at Visit 3 (Day 29) by Treatment Group - CC Population

Treatment Group	Number of Subjects with Microbiologic Cure n	Number of Subjects N	Proportion of Subjects with Microbiologic Cure	Proportion of Subjects with Microbiologic Cure 95% CI	Difference in Proportion of Subjects with Microbiologic Cure between Doxycycline and Azithromycin	Difference in Proportion of Subjects with Microbiologic Cure between Doxycycline and Azithromycin 95% CI	Test Statistic	Critical Value	P-Value ^a
Doxycycline	x	x	0.xx	0.xx, 0.xx	0.xx	0.xx, 0.xx	x.x	+/- 1.97743	0.xxx
Azithromycin	x	x	0.xx	0.xx, 0.xx					
All Subjects	x	x	0.xx	0.xx, 0.xx					

Note: The denominator for proportions is based on the number of subjects enrolled in the respective treatment group.

^a P-value from the two-sided Pearson Chi-Square test.

Implementation Notes:

Depending on the observed test statistic value, the last two columns will be rounded accordingly. The appropriate critical value (positive vs. negative) will be displayed according to the sign of the test statistic.

Tables with similar format:

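### The cure-table denominator note fits only 2 of 24 SAP tables, and the antibiotic failure rule is missing from the cure definition the primary analysis cites

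*SAP*

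**What the plan says.** **Denominator.** The shell for Table 13 (primary analysis, CC) carries the note "The denominator for proportions is based on the number of subjects enrolled in the respective treatment group". The Table 19 shell (CC by LGV status) repeats it, and Tables 14-18 and 20-36 are listed as having a similar format. Table 7 shows what enrolled means: "N=Number of enrolled subjects randomized to the specified treatment group". The disposition shell (Table 9) likewise puts enrolled and randomized in one row. SAP 6.1 states a different basis: "The frequency and percentages (based on the sample size) of observed levels will be reported for all categorical measures". The 6.1.1 code, "Table treatment*analysisvariable / binomial(wilson"), takes the proportion and its interval from the same records.

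**Cure status.** SAP 3.3.1 opens with "Microbiologic cure will be based on rectal CT NAAT results", and Tables 1 and 2 then classify by NAAT result alone. SAP 8.1 and 8.2.1 each say "See Section 3.3.1 for the definition of microbiologic cure". The antibiotic rule is in 6.3.2.4: recipients before the visit "will be included in ITT and CC analyses as treatment failures and reviewed by the blinded case committee for inclusion in PP analyses". Protocol 10.4.1.3 has the same rule: they "will be included in ITT and CC analyses as microbiologic failures and reviewed by the blinded case committee for inclusion in PP analyses".

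**Membership.** SAP 6.3.2.2 requires microbiologic data from the visit for CC, and 6.5 excludes unknown cure status from CC and PP while imputing failure in ITT. SAP 6.3.2.3 lists receipt of a CT-active antibiotic as a PP exclusion. SAP 6.3.2.4 gives the blinded committee case-by-case authority over PP.

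**The concern.** The primary results table should have one denominator and the primary endpoint one derivation. Here the note under the primary table names all randomized subjects, while the table's title names a population that leaves some of them out. A programmer who derives cure from the section that 8.1 and 8.2.1 cite would also never meet the antibiotic rule. Recipients stay in follow-up (Protocol 6.5, SAP 4.4.7), so a recipient with a negative Day 29 NAAT is a case that can occur: Cure by Table 1, failure by 6.3.2.4.

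The note puts the reported proportions at stake. The cure-status gap bears on who counts as cured in the CC test at both formal looks, and in ITT. The CC membership conflict bears on who is counted in that test. The PP conflict is outside the primary analysis.

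**Working it through.** **Inputs.** Enrollment target 274, at least 90% evaluable, about 246 in the primary analysis, planning cure rates 95% and 85% (SAP 5); 1:1 allocation (SAP 4.4.3); final bound 1.97743 (SAP 8.2.1). The plan's own figure reproduces: 0.9 × 274 = 246.6, stated as approximately 246. Per arm that is 137 enrolled and 123 in CC. Rounded to whole subjects, 0.95 × 123 gives 117 cures and 0.85 × 123 gives 105.

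**1. Which tables the note fits.** Tables 13-36 are 24 tables.
- Overall ITT (14, 17): enrolled equals ITT, so the note is right.
- Overall CC and PP (13, 15, 16, 18): the note contradicts the population.
- CC and PP subgroup tables (12 of Tables 19-36): it contradicts the population and omits the subgroup.
- ITT subgroup tables (20, 23, 26, 29, 32, 35): the population agrees, but the subgroup is omitted.

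The note is therefore wrong for 4 + 12 + 6 = 22 tables and right for 2.

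**2. Size if the note were followed.**

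| | CC denominator | Enrolled denominator |
|---|---|---|
| Doxycycline | 117/123 = 0.951 (Wilson 0.898-0.977) | 117/137 = 0.854 |
| Azithromycin | 105/123 = 0.854 (Wilson 0.781-0.905) | 105/137 = 0.766 |
| Difference | 12/123 = 0.098 | 12/137 = 0.088 |

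Both enrolled-based proportions fall outside the CC Wilson limits that would be printed beside them. In a CC subgroup table with subgroup share f of the arm (assumed, since the documents give none), a true 0.95 would print as 0.95 × f × 246/274: 0.085, 0.213 and 0.426 for f = 0.10, 0.25 and 0.50.

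**3. Cure status of a NAAT-negative recipient.** SAP 3.3.1 gives Cure. SAP 6.3.2.4 and Protocol 10.4.1.3 give failure in ITT and CC. The documents give no number of recipients, so the following is a range, not an estimate. With pooled Z = (p1 − p2) / √[p(1 − p)(2/123)], 117 v 105 gives 2.578.
- None recoded: no change.
- 1, 2, 4, 8, 10 recoded to failure in each arm: 2.489, 2.409, 2.274, 2.073, 1.996, all above 1.97743. With 11 per arm: 1.962, below it.
- Three in total, with 3, 2, 1 or 0 of them in doxycycline: 1.836, 2.244, 2.652, 3.060. Only the first split crosses the bound.

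**4. Recipient without a visit NAAT.** SAP 6.3.2.4 includes him in CC as a failure; 6.3.2.2 and 6.5 leave him out. In ITT he is a failure under either text. Adding 1, 2 or 4 such subjects per arm to CC as failures gives Z = 2.487, 2.407, 2.269.

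**5. PP.** SAP 6.3.2.3 excludes recipients outright, while 6.3.2.4 sends them to the committee for possible inclusion. Protocol 10.4.1.2 and 10.4.1.3 differ in the same way. No text says which prevails or how a retained recipient is scored. Table 7 still lists treatment for another symptomatic STD and exposure to an STD as PP exclusions, although 6.3.2.3 no longer does. SAP 15 discloses that the criteria changed, but the shell was not updated.

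**The case against.** The strongest reply is that a careful analyst would get all of this right. Each cure table names its population and prints N beside n, 6.1.1 computes from the analysed records, 8.2.1 runs the test in CC, and interim Table 12 has no such note. The antibiotic rule is prespecified in both documents, names ITT and CC, and as the specific rule naturally qualifies the general NAAT table. Recipients should be few, because these drugs are prohibited during participation and avoided where a suitable alternative exists. The committee's authority may be the intended answer for PP.

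Most of that stands and limits the point to a wording correction. What remains is that the texts conflict as written, and no passage says which governs.

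Two stronger readings are tempting, and the documents support neither.
- A reader might put 137 per arm into the test, get Z = 1.85, and infer that the note could cost the trial its result. The note concerns proportions; the planned test runs in CC.
- A reader might infer from the three-recipient example that the rule biases against doxycycline. That is one extreme split. Splits with one or none of the three in doxycycline raise Z, and nothing in the documents indicates how recipients would divide.

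**Conclusion.** The point holds as a minor wording correction that touches the primary results table and the derivation of the primary endpoint. The denominator note is wrong for 22 of 24 tables: it contradicts the population in the CC and PP tables, and it omits the subgroup in every subgroup table, including the six ITT ones. Followed literally, it would understate the planning proportions by about 0.10 and 0.09, with no effect on the chi-square test. These figures assume 137 enrolled and 123 in CC per arm.

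The failure rule exists but is missing from the cure definition that 8.1 and 8.2.1 cite. Its numerical effect is unknown because no recipient count is given; it is zero if there are no NAAT-negative recipients. The CC membership conflict is narrow, and the PP conflict is secondary.

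**What to change.** Make four SAP edits before unblinding.

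1. Change the note for Tables 13-36 to: number of subjects in the specified analysis population (and subgroup, where applicable) in the treatment group.
2. Add an override to SAP Tables 1 and 2, with a cross-reference in 8.1 and 8.2.1, limited to ITT and CC: a non-study CT-active antibiotic after the first dose and before the visit counts as Failure, whatever the available NAAT result. The limit matters because Tables 1 and 2 also supply cure status for the PP tables. Without it, a recipient whom the committee keeps in PP would automatically become a failure, which neither document states.
3. State in 6.3.2.4 that in CC the rule applies only to subjects who otherwise meet the CC definition, including an available visit NAAT. The others are failures in ITT under 6.5.
4. Reconcile 6.3.2.3, 6.3.2.4 and the Table 7 PP rows into one PP rule. Say whether the exclusion or the committee decision prevails, and how any retained recipient is scored.

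Optional: add a derived cure-status column to Listing 6. Scoring can already be checked by joining it to Listing 10 on Subject ID.

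The cost is SAP wording and table notes. Edits 1 to 3 leave the CC definition, the failure rule, the test and the protocol unchanged. Edit 4 requires a decision on PP, outside the primary analysis.

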10.2 Sample Size Considerations

The sample size is derived from power calculations for a two-staged group sequential design with one unblinded interim analysis of the primary outcome halfway through the trial and the final analysis after the trial has been completed.

O'Brien-Fleming boundaries will be used for the interim and final analyses to control the overall Type I error of the trial at 5%. The choice of O'Brien-Fleming is motivated by the desire to stop the trial early only if the interim difference in cure rates between treatment groups is large, and to continue in the presence of a moderate or small interim difference. For the calculations, it was assumed that the interim analysis will occur when 50% of the planned number of primary analysis-eligible subjects have been enrolled and followed through Day 29.

The sample size for the study was updated from the original target due to logistical and feasibility reasons. The enrollment target is 274 subjects. Based on previous prospective studies of MSM recruited from the PHSKC STD clinic [10-13], it is anticipated that at least 90% of enrolled subjects will be eligible for the primary analysis population; therefore, it is expected that 274 enrollments will lead to approximately 246 subjects eligible for the primary analysis.

Previously reported cure proportions have generally ranged 95-100% for doxycycline and 74-92% for azithromycin [14-20]. The 246 primary-analysis-eligible subjects along with the O'Brien Fleming boundaries will provide 75-80% power to detect a 10% difference in cure rates between treatments using conservative estimates of treatment-specific cure rates based on the literature (~95% cure rate for doxycycline and ~85% cure rate for azithromycin). The study will have more than 80% power to detect a 10% difference across a range of cure rates of doxycycline and azithromycin consistent with rates calculated in a meta-analysis of the efficacy of azithromycin and doxycycline for the treatment of rectal chlamydia infection [9]. See Table 1 below for power estimates.

Table 1: Power available to detect a 10% difference in cure proportions between treatments detectable with total sample size of N = 246 and interim analysis at N = 123

Cure Proportion		Power
Doxycycline	Azithromycin	
95%	85%	75%
96%	86%	79%
97%	87%	83%
98%	88%	87%
99%	89%	92%

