10.4.1.2 Efficacy Analyses

Intent-to-Treat (ITT) Population: This analysis population includes all randomized subjects.

Complete Case (CC) Population: This analysis population includes all randomized subjects who meet all inclusion/exclusion criteria at enrollment, have a positive baseline rectal CT NAAT result, and have post-baseline microbiologic data available. For analyses at Day 15, microbiologic data must be available from the Day 15 visit. Likewise, for analyses at Day 29, microbiologic data must be available from the Day 29 visit.

The CC population will be the primary efficacy analysis population.

Per-Protocol (PP) Population: This analysis population includes all randomized subjects who meet all inclusion/exclusion criteria at enrollment, have a positive baseline rectal CT NAAT result, have post-baseline microbiologic data available, sufficiently adhere to the study drug regimen (defined below), and do not experience any of the following after enrollment and before a particular visit (Day 15 for analyses at Day 15, and Day 29 for analyses at Day 29):

- Receive treatment for a symptomatic STD other than CT
- Exposure to an STD
- Receive treatment with an antibiotic active against CT
- Have condomless receptive anal sex

For analyses at Day 15, microbiologic data must be available from the Day 15 visit. Likewise, for analyses at Day 29, microbiologic data must be available from the Day 29 visit.

A subject is considered sufficiently adherent with study treatment if he takes the initial dose of azithromycin (or placebo) and initial dose of doxycycline (or placebo) in the clinic (or at retreatment within 48 hours, if applicable) and at least 9 additional doses of doxycycline (or placebo) within 10 days (inclusive) of the initial completed dose (or of the completed retreatment dose, if applicable). Assessment of subject adherence to study treatment is described in Section 6.4.

Alternative definitions of compliance and analyses of adherence will be explored; details will be provided in the SAP.

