6.3.2.3. Per-Protocol (PP) Population

The Per-Protocol (PP) Population includes all randomized subjects who meet all inclusion/exclusion criteria at enrollment, have a positive baseline rectal CT NAAT result, have post-baseline microbiologic data available, sufficiently adhere to the assigned study drug regimen (defined in Section 3.3.4), and do not experience either of the following after enrollment and before a particular visit (Day 15 for analyses at Day 15, and Day 29 for analyses at Day 29):

- Receipt of an antibiotic active against CT
- Have condomless receptive anal sex

For analyses at Day 15, microbiologic data must be available from the Day 15 visit. Likewise, for analyses at Day 29, microbiologic data must be available from the Day 29 visit.

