8.2. Final Analysis

8.2.1. Primary Efficacy Analysis

The primary efficacy endpoint for the final analysis is the proportion of subjects with microbiologic cure in each study arm at Day 29. See Section 3.3.1 for the definition of microbiologic cure.

A test of hypothesis comparing the proportion of subject with microbiologic cure at Visit 3 (Day 29), will be conducted in the CC population. The null hypothesis for the comparison is that there is no difference in proportions between treatment arms, with a two-sided alternative that considers the possibility of a difference in either direction. The test will be conducted using a Pearson Chi-Square test at the 5% two-sided significance level. The number of subjects, the proportion of subjects with microbiologic cure, and the 95% Wilson confidence interval for the proportion of subjects with microbiologic cure will be presented overall and by treatment group. In addition, the difference in proportions between the Azithromycin group and the Doxycycline group and 95% Wilson confidence intervals will be presented.

The test statistic will be compared to the O'Brien Fleming bound calculated in the study's sample size calculations to determine significance. At the final analysis the bound is |1.97743|, thus if the test statistic is either greater than 1.97743 (doxycycline cure rate is higher than azithromycin cure rate) or less than -1.97743 (azithromycin cure rate is higher than doxycycline cure rate), then the resulting interpretation is that the cure rates are significantly different between arms. Otherwise, the resulting interpretation is that the cure rates are not significantly different between arms.

The above analyses, apart from the O'Brien Fleming bound comparisons will be repeated in the ITT and PP analysis populations.

See [Table 13](#), [Table 14](#), and [Table 15](#). See Section 6.1 for pseudocode to fit the above analyses. Individual efficacy response data is presented in [Listing 6](#).

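### The per-protocol set drops anyone given a CT-active antibiotic whatever the indication, so re-treatment for persistent rectal CT becomes an outcome-dependent exclusion with no stated PP outcome rule

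*SAP*

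**What the plan says.** The CC population is primary. SAP 8.2.1 repeats the analysis in the intention-to-treat (ITT) and PP populations without the O'Brien-Fleming comparison.

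Three rules meet when a man receives a CT-active antibiotic after enrollment and before the visit analyzed:

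- **ITT and CC scoring.** SAP 6.3.2.4 says such men, whatever the reason for the antibiotic, "will be included in ITT and CC analyses as treatment failures and reviewed by the blinded case committee for inclusion in PP analyses". Protocol 10.4.1.3 has the same rule. It names no PP outcome.
- **PP membership.** SAP 6.3.2.3 lists "Receipt of an antibiotic active against CT" as an event that removes a man from PP. Protocol 10.4.1.2 has "Receive treatment with an antibiotic active against CT". Neither is limited by indication.
- **Outcome by default.** SAP Table 1 (section 3.3.1) classifies Day 29 status from NAAT results alone. Positive at Day 15 and negative at Day 29 is read as delayed RNA clearance and scored cure.

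SAP 6.3.2.4 lets the case review committee decide PP inclusion, censoring and further analysis requirements case by case. It adds: "The committee will be blinded to both treatment group and outcome status for each case".

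**The concern.** A PP exclusion for another active drug is ordinary when the drug was given for something else. It is different when the drug was given because the study treatment failed. Removing that man selects on the outcome, and keeping him under Table 1 can turn a failure into a cure through the second drug. Either way the PP cure rate rises, and it rises more in the arm with more failures.

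At stake is how the PP repeat is read beside the primary result. If doxycycline is better, PP would be pulled toward no difference and could look like weaker support for the CC finding than the data warrant.

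**Working it through.** **1. The plan's own figure.** Inputs: 123 per arm (246 evaluable, 1:1), the "Pearson Chi-Square test at the 5% two-sided significance level", bounds 2.79651 (SAP 8.1) and 1.97743 (SAP 8.2.1), and cure rates 97% and 87% (SAP section 5). The final drift is 0.10 / √[(0.97×0.03 + 0.87×0.13)/123] = 0.10/0.0340 = 2.94; the interim drift is 2.94/√2 = 2.08. The bivariate normal with correlation √0.5 gives power 0.834 (0.821 with pooled variance) against the stated 83%. The bounds give overall alpha 0.0500. The plan's figures reproduce and are not in dispute.

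**2. Which arm loses failures.** If the same share r of failures is re-treated in each arm, azithromycin's part of those lost is its part of all failures: 15/(5+15) = 75% at 95/85, and 13/(3+13) = 81% at 97/87.

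**3. Effect on the PP difference.** Take 95/85 rounded to whole men: 6 doxycycline and 18 azithromycin failures of 123 each. Assume no other PP losses.

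- CC: 18/123 − 6/123 = 0.0976. The pooled failure rate is 24/246, so z = 0.0976 / √[0.0976×0.9024×(2/123)] = 2.58.
- PP, removed: 18(1−r)/(123−18r) − 6(1−r)/(123−6r), with pooled z. At r = 10% this is 16.2/121.2 − 5.4/122.4 = 0.0895.
- PP, all kept and all scored cure: 0.0976(1−r), with pooled z.

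The documents give no r, so a range is shown:

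| r | Failures lost, doxycycline / azithromycin | Removed: points (z) | Kept as cure: points (z) |
|---|---|---|---|
| 0 (CC) | 0 / 0 | 9.76 (2.58) | 9.76 (2.58) |
| 10% | 0.6 / 1.8 | 8.95 (2.46) | 8.78 (2.43) |
| 25% | 1.5 / 4.5 | 7.69 (2.26) | 7.32 (2.20) |
| 33% | 2.0 / 5.9 | 6.98 (2.15) | 6.54 (2.07) |
| 50% | 3 / 9 | 5.39 (1.87) | 4.88 (1.78) |

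**4. The same at 97/87.** With men removed, the expected difference is 9.1, 7.8 and 5.4 points at r = 10%, 25% and 50%. Fixed-sample power at two-sided 5% is 0.79, 0.72 and 0.55, against 0.83 at r = 0.

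**5. The opposite case.** If CT-active antibiotics are unrelated to cure and equally common in both arms, removal leaves the PP difference at 10 points. The CC failure rule then shrinks its own difference: at an assumed 5% use, 0.95 × 10 = 9.5 points. The bias in step 3 comes only from re-treatment for persistent rectal CT.

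**The case against.** **The route is narrow, and this stands.** Protocol section 4 and 7.4 tie referral for treatment to a positive or indeterminate NAAT at the final visit, and describe no action on a positive Day 15 result. CT-active antibiotics are prohibited during participation, with alternatives preferred where suitable (Protocol 6.5). A man treated after a positive early-termination swab with no Day 29 result fails the data requirement of both CC and PP. What remains is mainly the unscheduled visit for symptoms, where a swab may be taken (Protocol 7.6). Nothing in the documents supports r of 25% to 50%.

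**A reader might infer that re-treatment can never make a man a PP failure.** The documents do not support that. The committee's power to set further analysis requirements allows failure scoring; the SAP just does not direct it.

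**A reader might infer that outcome blinding stops the committee from telling re-treatment for rectal CT from other antibiotic use.** That is not supported either. The committee reviews concomitant infections and medications, Listing 10 records the indication, and no text withholds it.

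**A reader might call every lost man a true failure.** Table 1 itself allows for delayed RNA clearance, so some men positive at Day 15 could have cleared without a second drug.

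**The effect is visible, which stands in part.** Table 7 counts PP exclusions for this reason by arm, and Listings 1 and 10 give reasons and indications by subject. That lets a reader find the problem; it does not put the PP estimate right.

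**Conclusion.** The point holds as a defect in a supportive analysis. The written PP rule excludes on an event that, for men re-treated for persistent rectal CT, is a consequence of treatment failure; for men kept, the default scoring can read the second drug's effect as cure. Under the plan's cure rates and equal r, 75% to 81% of the failures lost would be azithromycin, so the PP difference moves toward zero.

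The size rests on assumptions the documents do not supply: r, its equality across arms, and 123 men per arm in PP. At r = 10% the loss is 9.76 − 8.95 = 0.81 points. With men removed, z is still 2.15 at r = 33% and falls below 1.96 only by r = 50%. A PP result that appears to contradict a positive CC result therefore needs a re-treatment share that the described procedures make unlikely. The primary CC test is unaffected by this PP handling. The change is worth making because it is cheap and replaces case-by-case discretion with a stated rule.

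A neighboring gap should be reconciled: SAP 6.3.2.4 includes antibiotic recipients in CC as failures, while 6.3.2.2 requires a Day 29 NAAT for Day 29 CC analyses. A re-treated man without that NAAT falls under both.

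**What to change.** In the SAP:

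- In 6.3.2.3, limit the PP antibiotic exclusion to CT-active antibiotics given for an indication other than rectal CT.
- State that an otherwise PP-eligible man given a CT-active antibiotic for rectal CT after a positive post-baseline rectal NAAT stays in PP and counts as a failure at later visits, as in CC and ITT.
- Leave men treated on symptoms alone, without a positive NAAT, to the blinded committee.
- Derive the flag by program from the recorded indication (Listing 10) and the NAAT data, outside the committee, so its blinding to outcome is kept.
- Tabulate recipients of CT-active antibiotics by arm and indication.

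The cost is SAP wording, one derived flag and one small table, all from data already collected. No treatment or follow-up procedure changes. The downside is that some men with delayed RNA clearance or a presumed new infection would count as PP failures, as they already do in CC and ITT.
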